## PROTOCOL

Neurosteroids as Novel Therapeutic Agents for PTSD in OEF/OIF/OND Veterans  
PI: [name], PhD

without the written consent of the patient. All clinical and biological data obtained from research interviews and the laboratory will be deidentified. The data will be kept in locked file cabinets and accessible only to qualified research personnel. Only coded study numbers will appear on data and documents used for evaluation or statistical analysis. In addition, any publications resulting from this research will not identify individual participants.

### 3. Risks for Study Personnel.

There is minimal risk involved to study personnel. A trained laboratory phlebotomist will draw patient blood for laboratory analysis and serum/blood storage. There is a slight risk of potential needle stick, however the Durham VA Chemical Laboratory provides extensive risk prevention training for all phlebotomists, thus the likelihood of an accidental needle stick is low. The blood samples will be transported to -80° freezer for storage by study personnel. In order to reduce the risk of direct exposure, personnel will wear personal protective equipment while transporting patient serum/blood

### C. Potential Benefit of the Proposed Research to the Participant and Others.

While study participants may not receive benefits from the proposed research other than monetary compensation (\$75 per visit), their participation may lead to a better understanding of their symptomatology. A travel stipend will also be provided (averaging \$15, depending upon distance traveled).

For those not currently treated, study participation may lead to referral for treatment upon completion (or withdrawal) of the study. In terms of benefit to others, knowledge gained from the study may help the evaluation and treatment of patients with PTSD and co-occurring symptoms in the future. No serious adverse events have been attributed to DHEA to date.

### **Selection of Subjects**

Forty OEF/OIF/OND Veterans with PTSD between the ages of 18-65 will be randomized. Both male and female subjects and all ethnic groups will be eligible to participate in this study. All subjects will be currently experiencing PTSD, as evidenced by a CAPS-5 score that is  $\geq 33$  at baseline. We chose a CAPS-5 score of  $\geq 33$  after review of the available limited literature on this area. For example, a recent poster presented at the American College of Neuropsychopharmacology (ACNP) provided for rationale on use of CAPS-5 score of  $\geq 29$  for non-combat PTSD vs  $\geq 33$  for combat PTSD (Sullivan, G et al., 55th Annual Meeting; ACNP, December 7, 2016). We anticipate that a number of participants will have co-occurring depression symptoms and a history of mild TBI (mild TBI and major depression are not exclusionary); we will thus control for the presence of major depression and a history of mild TBI in the statistical analysis. Patients who have a history of moderate or severe TBI will be excluded. Veterans will be recruited from the Durham VA Medical Center and VA Mid-Atlantic MIRECC Repository and Post-deployment Health Study in OEF/OIF/OND Veterans. This Repository has enrolled over 3,200 OEF/OIF/OND Veterans to date, and

## PROTOCOL

### Neurosteroids as Novel Therapeutic Agents for PTSD in OEF/OIF/OND Veterans

PI: [name], PhD

over 94% of these participants have provided permission to be re-contacted for future research studies such as the one proposed.

**Inclusion of Women and minorities:** Women comprise a significant proportion of the Veteran population and will be recruited into the proposed study at a rate expected to match the standard female percentage in the Veteran population. In addition, minorities will also be included similarly. We estimate that our study population will be approximately 20% female and approximately 40% African American (based upon demographics of the VA Mid-Atlantic MIRECC Repository and Post-Deployment Mental Health Study).

#### Inclusion Criteria:

1. OEF/OIF/OND era Veterans, 18-65 years of age,
2. PTSD diagnosis (CAPS-5 score  $\geq 33$ ).
3. Negative pregnancy test if female. Sexually active subjects are required to use a medically acceptable form of birth control if they are of childbearing potential and could become pregnant during the study. A medically acceptable form of birth control includes non-hormonal intrauterine devices, surgical sterilization, or double barrier methods (e.g., diaphragm with contraceptive jelly, condom with contraceptive foam, cervical caps with contraceptive jelly). Sexual abstinence with agreement to continue abstinence or to use a medically acceptable method of contraception should sexual activity occur is permissible.
4. Female participants must have had a normal mammogram within the last year (if older than 40)
5. Female participants must have had a normal pelvic exam within the last year
6. No change in medications less than 4 weeks before baseline assessment.
7. No anticipated need to alter medications for PTSD for the 6-week study duration (as determined by study physician's review of records and/or discussion with prescribing physician).
8. Ability to fully participate in the informed consent process.

#### Exclusion Criteria:

1. Unstable medical or neurological illness, including seizures, renal impairment or CVA and inability to participate in neuroimaging (fMRI).
2. Use of oral contraceptives or other hormonal supplements, as it is unclear if DHEA metabolism to other neurosteroids such as estradiol may potentially impact contraceptive efficacy.
3. Significant suicidal or homicidal ideation.
4. Current DSM-5 diagnosis of bipolar disorder, schizophrenia, or other psychotic disorder (including major depression with psychotic features), or cognitive disorder due to a general medical condition.
5. Female patients who are pregnant or breast-feeding.
6. Known allergy to study medication.
6. History of moderate or severe TBI.

## PROTOCOL

### Neurosteroids as Novel Therapeutic Agents for PTSD in OEF/OIF/OND Veterans

PI: [name], PhD

7. Substance dependence within past three months, per DSM-5 criteria (excluding caffeine and nicotine).
8. Abnormal prostate specific antigen (PSA; >2.5ng/ml in males age 49 or less; >4ng/ml in males age 50 or greater) or history of prostate cancer, breast cancer, or uterine cancer.
9. A family history of prostate, breast or endometrial cancer in a first-degree relative
10. Presence of any factors/conditions, medical or non-medical, that may interfere with conduction of study assessments in the judgment of the study team,
11. Serious or unstable cardiovascular, hepatic, renal, metabolic, respiratory, or hematologic illness, symptomatic peripheral vascular disease, or other medical condition or psychiatric conditions or behaviors that would compromise participation and/or likely to lead to worsening of symptoms during the course of the study in the opinion of study physician and research team.
12. Are non-ambulatory or require the use of crutches or a walker.
13. Taking Narcotic medications or benzodiazepines for any reason.

### Subject Recruitment

Participants will be recruited from Durham VA IRB-approved local advertising (flyers), by referral from their Durham VA medical and behavioral health providers and from the OEF/OIF/OND cohort who previously participated in the PDMH study. We will obtain contact information from the VISN 6 MIRECC Data Repository (Repository) (which currently contains 3,200 OEF/OIF/OND Veterans; over 94% of these Registry participants have already provided permission to be re-contacted for future research studies) that contains contact information provided by participants at the time of their PDMH Study participation. Prospective participants will be sent Durham VA IRB-approved letters and follow-up phone calls utilizing a Durham VA IRB-approved phone script.

Once an individual has been successfully contacted, research staff will read a brief script introducing the study and providing context related to the participant's previous enrollment in the PDMH Study. Early in this script, the individual will be asked if they are interested in hearing about the current study. If the individual is not interested, they will be thanked for their time and the call will end. If the individual is interested, the remainder of the script will be read providing information about what activities will occur should the individual choose to participate. Any questions regarding participation will be answered. If the participant wishes to participate, they will then be rescheduled to report in-person to complete the study. Additionally, decision-making capacity will be evaluated by consulting clinical records (if available) and by asking the patient if they have a legal guardian. Individuals without decision-making capacity and/or with a legal guardian will not be contacted.

, for a target number of 40 randomized participants; of these 40 randomized participants, it is estimated that at least 32 participants will receive at least one study visit following randomization (20% drop-out assumed).

## PROTOCOL

Neurosteroids as Novel Therapeutic Agents for PTSD in OEF/OIF/OND Veterans  
PI: [name], PhD

### Consent Process

The informed consent process, including completion of the Informed Consent and HIPAA forms will occur in a private room at the Durham VA Health Care System and will be completed prior to the initiation of any study activities. The informed consent process will be conducted by a member of the research team who has been trained in the proper procedures and language to be used so as to minimize the possibility of coercion or undue influence and to ensure that the individual understands the information being provided

A participant who is judged likely to meet all of the inclusion criteria and none of the exclusion criteria will meet with a member of the research team to discuss the research protocol, and to determine if the patient is capable of providing informed consent. Individuals without decision-making capacity will not be enrolled. Eligible participants will be provided with a description (verbal and written) of the informed consent form, which includes the risks along with procedures to minimize these risks, and the participants' rights and responsibilities. Participants will be given the opportunity to read the consent form and ask questions. Participants will be assured that participation in this research study is voluntary and that they may withdraw from the study at any time without adversely affecting their medical care or any benefits they might be receiving. They may also refuse to answer any research questions during the interview. Participants who are eligible for the study and choose to participate will sign the consent form in the presence of a member of the research team.

### Digital Audio-recording:

Participants will be explicitly asked for permission to digitally audio-tape CAPS-5 interviews in the IRB-approved written Informed Consent Form. Participants will be informed that audiotaped sessions may be reviewed by an expert ([name]) for the purposes of interviewer fidelity. We anticipate that the expert will review CAPS-5 interviews of the first 2 participants seen by each assessor, and 1-2 randomly selected interviews every 3-6 months. Digital audio recordings and corresponding CAPS-5 assessments will be identified only by subject ID and stored on the S-drive, behind the VA firewall at S:\MIRECC\Collaborators. Audio recordings will be captured using a Philips Pocket Memo Voice Recorder DPM8000 or other approved audio recorder. Only approved study staff and the expert reviewer will have access to this file path/folder. No other portion of study visits will be recorded.

### Study Interventions

We will conduct a parallel-group, double-blind, placebo (PBO)-controlled, randomized Phase 2 pilot study with 400mg DHEA to test whether we can establish proof of concept (POC) for this agent. 40 OEF/OIF/OND Veterans with PTSD will be randomized to receive a one-time oral adjunctive treatment with DHEA or PBO in the fMRI paradigm (same day). Participants will then continue to receive a 6-week sustained treatment of DHEA or PBO. To establish POC, we seek to determine whether DHEA is superior to

## PROTOCOL

Neurosteroids as Novel Therapeutic Agents for PTSD in OEF/OIF/OND Veterans  
PI: [name], PhD

PBO on neural circuits related to fear-anxiety-emotional regulation. We will determine potential fear-anxiety circuit target engagement following one-time oral adjunctive dose of DHEA (400 mg) using a same-day fMRI paradigm (the SEAT procedure, see below) to assess derived functional connectivity measures between the amygdala and the hippocampus as compared to PBO (primary outcome). Further, we will also determine if fMRI and serum neurosteroids (DHEA, DHEAS, androsterone, and/or other neurosteroids) may be candidate biomarkers of PTSD symptoms (CAPS-5) that predict therapeutic response to a DHEA intervention (secondary outcomes). The proposed set of studies will enable us to investigate these neurosteroids as novel pharmacological interventions for PTSD, and to identify biomarkers of therapeutic response in PTSD. Finally, as an exploratory goal, the current study will determine if treatment with DHEA impacts myelin integrity (as assessed by STI), and if peripheral neurosteroid levels are potentially associated with myelin content, other neuroimaging parameters, or therapeutic response.

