The majority of research in Veterans with PTSD that has focused on white matter assessment has utilized diffusion tensor imaging (DTI). Reductions in fractional anisotropy in cingulum (white matter fibers that project from the amygdala to prefrontal cortex; involved in emotion processing) and other areas near the prefrontal cortex (Kim et al., 2005; 2006; Schuff et al., 2011; Zhang et al., 2011) have been reported in patients with PTSD. Overall, however, DTI studies in PTSD have been somewhat mixed (Daniels et al., 2013 review). Technological limitations of DTI may be contributing to these disparate results among PTSD investigations, as DTI lacks the resolution and sensitivity required for the optimal assessment of white matter microstructure (Cao et al., 2014). As an exploratory aim, we are thus proposing to use a new neuroimaging technology - quantitative susceptibility mapping and susceptibility tensor MRI (QSM/STI), which provides superior resolution and sensitivity to non-invasively assess *in vivo* fiber tract alterations in Veterans with PTSD. This is a promising new technology created by our collaborator at Duke, [name].

**Significance:** This project may lead to a novel new therapeutic for OEF/OIF/OND Veterans with PTSD that is safe, efficacious, inexpensive, and well-tolerated. It could also identify serological and/or neuroimaging biomarkers for therapeutic response, potentially leading to personalized treatments for Veterans with PTSD. There is currently a paucity of safe and effective pharmacological agents for the treatment of PTSD, a disorder that impacts large numbers of OEF/OIF/OND Veterans and is frequently accompanied by co-occurring conditions that include depression and TBI. DHEA may be a promising new therapeutic in PTSD, as it demonstrates anti-anxiety effects in rodent models and fear-anxiety circuit regulation in humans. Based on our

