### Tertiary Outcome Measures

Tertiary outcome measures will include: Radioimmunoassay for Neurosteroid quantifications of serum levels of DHEA, DHEAS, and androsterone. These neurosteroids will be correlated with symptomatic rating scales.

Exploratory Aim: To investigate if treatment with DHEA impacts myelin integrity (as assessed by susceptibility tensor imaging/STI), and to examine myelin integrity as a possible biomarker for PTSD treatment response. We will also determine if serum neurosteroid levels are correlated with neuroimaging parameters utilizing STI (QSM)

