## PROTOCOL

Neurosteroids as Novel Therapeutic Agents for PTSD in OEF/OIF/OND Veterans  
PI: [name], PhD

senior author on these pivotal trials and is a collaborator (please see accompanying letter) along with [name] who was a co-investigator and is the primary mentor for the CDA. Subsequent testing with functionally defined ROIs will be used to make statistical inferences about treatment response and to identify correlations with cognitive changes, CAPS-5 scores, and neurosteroid levels. In addition, we propose to study the correlation between PTSD symptom severity and disruption in fear systems interrogated by the task paradigms. This will be probed further by examining correlation between the hypothesized clinical behaviors and fear system activation during the associated task (e.g., severity of hypervigilance symptoms and activation. Correction for the family-wise error rate will be based upon the Gaussian random field (GRF) theory that is implemented in FSL (Worsley et al., 1996).

Primary outcome analyses will be based on maps of activation, reaction time, and on-line accuracy judgments via a 2 (drug type: DHEA or Placebo)  $\times$  3 (face type: angry, fearful, neutral)  $\times$  3 (condition: male/female, inside/outside, like/dislike) repeated-measures ANOVA for main effects and interactions. Follow-up effect analyses will be performed with two-tailed *t*-tests and significance threshold at 0.05 with correction for multiple comparisons. Z-score images from the individual activation maps will be entered in second-level random-effects analyses using SPM8 and corrected for multiple comparisons,  $p<0.05$ . Activation threshold and cluster size will be determined using AlphaSim (Ward, 2000) to correspond to a false-positive rate of  $p<0.05$ , corrected for multiple comparisons within ROIs. Voxel coordinates that will be reported will correspond to standardized MNI space. The time series from significant clusters within regions of group difference will be used in a psychophysiological interaction (PPI) analysis. Deconvolved time series in the anatomical right amygdala will be extracted for each subject and represent the first regressor in the PPI analysis (physiological variable). The experimental condition is the second regressor (emotion processing; psychological variable). The regressor of interest will be the interaction between the time series of the seed region and the experimental condition.

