Change in total DSM5-defined PTSD symptoms from pre- to post- treatment, as assessed by the CAPS-5, the gold standard method for assessing PTSD symptoms in pharmacological treatment trials; measurements will be gathered at two-week intervals beginning at baseline and continuing through Week 8. Measures of pre-post treatment differences at the four study intervals will be regressed on a dichotomous proxy measure denoting treatment status coded positive for subjects randomized to the DHEA condition. In addition to the treatment proxy, all models will include covariates for measurement interval (time), and an interaction term crossing the treatment proxy with time. Test of the secondary hypothesis will be based on a 1 df test of the contrast of difference between drug and placebo at the final time point (SAS: LSMESTIMATE statement). Specifically at Week 8, H0: LSMEdhea  $\geq$  LSMEplacebo versus Ha: LSMEdhea  $<$  LSMEplacebo. We hypothesize rejection of a null hypothesis positing that difference in PTSD symptoms from baseline will be equivalent or greater among subjects randomized to DHEA at the final time point in lieu of an alternative hypothesis positing a reduction in PTSD symptoms in the DHEA cohort relative to placebo.

Measures of serum levels of three neurosteroids: DHEA, DHEAS, and androsterone will also be analyzed. As above, the outcome measure will be the change in steroid level from baseline (i.e., following 2 week placebo lead in) to Week 8 with measurements at two-week intervals. Models will be estimated as described above with tests of the primary hypothesis based on a 1 df test of the estimated contrast of the difference between drug and placebo at the final time point. In all cases, the following hypothesis will be tested: H0: LSMEdhea  $\leq$  LSMEplacebo versus Ha: LSMEdhea  $>$  LSMEplacebo. Results for tests of Aim 2 will be adjusted for multiple comparisons using the method of Hochberg (1998).

As secondary test of the hypothesized association between change in PTSD status and change in neurosteroid levels, Week 8 changes CAPS-5 scores will be regressed on Week 8 change in neurosteroid levels. Models will include, as above, covariates for age, gender, smoking status, depression, TBI status, and a measure of the baseline level of the tested neurosteroid. Based

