## PROTOCOL

### Neurosteroids as Novel Therapeutic Agents for PTSD in OEF/OIF/OND Veterans

PI: [name], PhD

on anticipated collinearities between the dichotomous randomization proxy and change, models will initially be estimated without the former. A significant inverse association between change in steroid levels and change in CAPS-5 scores would support the hypothesized efficacy of DHEA as an adjunctive therapy in treating PTSD. As above, results would be corrected for multiple comparisons.

Tests of secondary measures will be conducted as described above. Thus, proposed measures will be regressed as change from baseline scores on a model controlling for the baseline level of the tested outcome measure, the dichotomous randomization proxy, and an interaction term crossing the latter with time. Tests will again be based on a 1 df test of the estimated contrast (LSME: see above) of the difference between drug and placebo at the final time point. Expectations are that change in adverse outcome measures will be significantly mitigated in the DHEA intervention arm; measures associated with salubrious outcomes will be, conversely, improved. All results will be adjusted for multiple comparisons.

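### The plan seeks markers that predict response to DHEA but specifies no comparison of marker-outcome slopes between arms, so a purely prognostic marker could be read as predictive.

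*Combined protocol and SAP*

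**What the plan says.** Study Interventions lists as a secondary question whether fMRI and serum neurosteroids "may be candidate biomarkers of PTSD symptoms (CAPS-5) that predict therapeutic response to a DHEA intervention (secondary outcomes". The Significance paragraph gives the intended use of such biomarkers: "potentially leading to personalized treatments for Veterans with PTSD". The exploratory aim under Tertiary Outcome Measures adds a plan "to examine myelin integrity as a possible biomarker for PTSD treatment response".

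The analyses offered for these aims are:

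- **Imaging** (Data Analysis and Statistical Considerations): region-of-interest measures are used "to identify correlations with cognitive changes, CAPS-5 scores, and neurosteroid levels".
- **Neurosteroids, tertiary outcome**: serum levels are correlated with the symptom scales.
- **Neurosteroids, regression** (Data Analysis and Statistical Considerations): "Week 8 changes CAPS-5 scores will be regressed on Week 8 change in neurosteroid levels". Covariates are age, gender, smoking, depression, TBI status and the baseline level of the steroid under test. Because collinearity with the randomisation indicator is expected, "models will initially be estimated without the former". No later model is described. The stated reading is: "A significant inverse association between change in steroid levels and change in CAPS-5 scores would support the hypothesized efficacy of DHEA".

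The planned interactions are of three kinds. The longitudinal outcome models have "an interaction term crossing the treatment proxy with time". The task ANOVA crosses drug, face type and condition. The PPI analysis has a seed-by-condition regressor. None crosses a marker with treatment arm.

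**The concern.** A marker predicts response to DHEA only if the DHEA-placebo difference in outcome depends on its value. That is a statement about two slopes, one per arm. A correlation pooled over arms, or taken in the DHEA arm alone, estimates something else: whether people with a higher marker value end up better, whatever they received. A marker of spontaneous or placebo improvement passes that test equally well.

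The randomised placebo arm is what allows the two to be told apart, and the planned marker analyses do not use it for that. At stake is the biomarker conclusion of a proof-of-concept trial, which would guide which markers go forward and whom a later trial enrols. The primary connectivity comparison and the CAPS-5 treatment contrast are not affected.

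**Working it through.** **Inputs from the documents.** 40 randomised, 32 analysed, about 16 per arm (Experimental Design; Data Analysis and Statistical Considerations); alpha 0.05. Check: 40 x (1 - 0.20) = 32. The statistics section attributes the same 32 to 10% drop-out, which would give 40 x 0.90 = 36; 32 is used here as stated. The plan gives no marker-outcome correlation, so all values of r below are assumptions. Tests are two-sided.

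**1. Purely prognostic marker, pooled test against interaction test.** Simulate a standard normal marker m and outcome y = -r m + sqrt(1 - r^2) e, with the same slope in both arms and no arm effect. Compare (a) y on m, pooled, with (b) y on arm, m and arm x m, testing the last term on 32 - 4 = 28 df.

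| assumed r | pooled test significant | DHEA arm only | marker x arm significant |
|---|---|---|---|
| 0.3 | about 40% | 22% | about 5% |
| 0.5 | about 85% | 53% | about 5% |
| 0.7 | over 99% | 90% | about 5% |

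The pooled rejections are true correlations, not false positives; the error would lie in calling them prediction of response to DHEA. With a Bonferroni correction for three steroids, the pooled figures fall to about 24% (r = 0.3) and 72% (r = 0.5).

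**2. The regression that is spelled out.** Here the tested term is steroid change, adjusted for baseline level. If only the pre-dose level is prognostic, the change coefficient is significant in 4% to 6% of trials (r = 0.3 to 0.7; assumed baseline-to-Week 8 marker correlation 0.5 to 0.8; assumed DHEA shift 0 to 4 SD). So the table does not apply to it. Its exposure is different:

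- Steroid change that tracks improvement in both arms would still be picked up.
- With arm left out, steroid change can stand in for arm. Suppose DHEA raises the steroid by 4 within-arm SD and lowers CAPS-5 by 0.5 to 1.0 SD (both assumed), with no link between the two within arms. A regression on the change term alone is then significant in 23% to 68% of trials. With arm included, the figure is about 5%.

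**3. What an interaction test could deliver.** At r = 0.5 in both arms, SE of the slope difference is approximately sqrt(2) x sqrt(1 - 0.25) / sqrt(15) = 0.32; simulation gives about 0.33 SD per SD. The 95% half-width is about 2.05 x 0.33 = 0.68.

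For power, take no correlation under placebo and r under DHEA. By Fisher z, power = Phi(atanh(r) / sqrt(2/13) - 1.96):

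- r = 0.3: Phi(0.310/0.392 - 1.96) = 12%; simulation 12%.
- r = 0.5: Phi(0.549/0.392 - 1.96) = 29%; simulation 27%.

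For 80% power, n per arm = 2 x ((1.96 + 0.84)/atanh(r))^2 + 3, which is 167 at r = 0.3 and 56 at r = 0.5.

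**4. Which markers exist before the dose.** The Schedule of Events has blood draws at Weeks 0 and 2, so a pre-dose serum value is available (the Week 2 draw only if taken before dosing). MRI is listed only at Weeks 2 and 8. Design, Aim 1, places imaging two hours after the randomised dose, although Purpose speaks of pre- to post-treatment change. A pre-dose fMRI or STI measure is therefore not clearly planned.

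**The case against.** The strongest reply is that the aim is modest and the trial small. The text speaks of candidate and possible biomarkers and of preliminary evidence for an association. Aim 3 uses the idea of prediction for steroid increases seen after treatment, which is an on-treatment marker rather than a baseline effect modifier. An interaction test at 16 per arm would seldom be informative. All of this stands, and it is why the request is for an exploratory estimate and for wording. It does not remove the mismatch: the secondary question is still framed as response to DHEA in particular and tied to personalised treatment, and low power is no reason to let a test of another question answer it.

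A reader might also infer several stronger things that the documents do not support:

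- *That the plan only correlates, ignores baseline marker values, or has no interaction except treatment by time.* The regression is covariate-adjusted, baseline steroid is in it as an adjustment covariate, and the fMRI analyses contain other interactions.
- *That every marker is measured at the same visit as the outcome.* The Week 2 scan and the blood draws before Week 8 come earlier than the Week 8 CAPS-5.
- *That the plan would report a prognostic marker as predictive.* It does not say so. The reading it does commit to, for the change regression, is support for efficacy, and the word used about omitting arm implies a later model with arm, though none is specified.

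**Conclusion.** The gap is real, and it concerns secondary and exploratory inference only. Nothing in the plan compares marker-outcome slopes between arms, so a marker that is merely prognostic could be taken to predict response to DHEA. How often depends on correlations the documents do not give. For an unadjusted pooled correlation at 16 per arm, the range is about 40% (r = 0.3) to 85% (r = 0.5) before multiplicity correction, against about 5% for marker by arm. It would be wrong to quote 85% as the error rate of the planned steroid regression; that model's weakness is on-treatment change that follows improvement in both arms or substitutes for the omitted arm. It would equally be wrong to expect the interaction test to settle the matter, since a non-significant result at this size excludes little.

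**What to change.** 1. For each serum neurosteroid drawn before the randomised dose (DHEA, DHEAS, androsterone), fit Week 8 CAPS-5 change on baseline CAPS-5, arm, marker and arm x marker. State which draw is used and that it precedes dosing. Report the interaction slope with its 95% confidence interval, labelled exploratory.
2. Reserve the statement that a marker predicts response to DHEA for that interaction. Call pooled correlations and change-on-change results associations.
3. Describe fMRI and STI markers as on-treatment associations unless a pre-dose scan exists. An arm interaction with a post-dose measure would not repair this, because the measure may itself be altered by treatment.

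The cost is three extra models on serum data the trial already plans to collect, and some wording. The price in interpretation is an imprecise estimate (SE about 0.33 SD per SD at r = 0.5), which can generate a hypothesis but not confirm or rule one out.
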